14.2 Clinical Laboratory Variables

Clinical laboratory tests are performed at Screening, Baseline, Week 3 and Week 6/ET visits.

Due to COVID-19 disruptions it is possible that some test results may be collected from a local laboratory. Local laboratory results and the associated normal ranges will be converted to SI units; the local laboratory results, in SI units, will then be normalized to central lab ranges to be included in summary data analysis together with the central laboratory results. The normalization will be performed using the following scale transformation equation:

$$s = L_{\cdot} + (-x) \frac{s - s}{x - x}$$

where s is the normalized individual laboratory value to be used for summary; x is the original value from the local lab; L_x and U_x are the lower and upper limits from the local lab; L_s and U_s are the lower and upper limits from the central lab.

For labs with only a single upper (or lower) limit, the following scale transformation equation will be used:

$$=\frac{s}{x}$$

where s is the normalized individual laboratory value to be used for summary; x is the original value from the local lab; U_s is the upper (or lower) limit from the central lab; U_x is the upper (or lower) limit from the local laboratory. Local laboratory results and normalized results will be included in data listings. Only central lab and normalized local lab results will be used for summary of change from baseline, shift, and potentially clinically important (PCI) analyses.

Clinical laboratory tests include the following:

• Clinical chemistry serum tests

- Sodium (Na), potassium (K), carbon dioxide (CO₂), chloride (Cl), phosphorus (P),
 calcium (Ca), blood urea nitrogen (BUN), creatinine (CR), glucose, albumin (ALB),
 total protein
- Alanine aminotransferase (ALT), aspartate aminotransferase (AST), gamma-glutamyl transpeptidase (GGT), alkaline phosphatase (ALP), total bilirubin (TBIL), lactate dehydrogenase (LDH)
- Lipid panel
 - Total cholesterol, high-density lipoprotein (HDL)-cholesterol, triglycerides, low-density lipoprotein (LDL)-cholesterol, cholesterol/HDL ratio, non-HDL cholesterol
- o HbA_{1c}
- o Magnesium (Mg), Vitamin B12 (only at Visit 1 [Screening])
- o Thyroid function tests (only at Visit 1 [Screening])
 - Thyroid stimulating hormone (TSH) and reflex free T4
- o Prolactin
 - Prolactin results should be blinded to the Investigator and the Sponsor after Baseline. Results will be monitored by an independent Medical Monitor from the Clinical Research Organization (CRO)
- Creatine kinase (CK)/creatine phosphokinase (CPK)
- Pregnancy test
 - A serum pregnancy test should only be performed at Visit 1 for women of childbearing potential
 - A urine pregnancy test should be performed at all designated visits after Visit 1 for women of child-bearing potential
 - If urine cannot be obtained in women of childbearing potential, a serum pregnancy test should be done in its place
- Hematology tests
 - o Complete blood count (CBC) including:
 - White blood cell (WBC) count
 - Complete differential (relative and absolute)
 - Hematocrit (Hct), hemoglobin, red blood cells (RBC), platelets

- Reticulocyte count
- Urinalysis
 - o Blood, RBCs, WBCs, protein, glucose, ketones, specific gravity, pH
- Urine toxicology (drug) screen
 - O Urine toxicology (drug) screen will test for controlled substances. The following controlled substances may be tested with a urine toxicology screen: amphetamine, barbiturates, benzodiazepines, cocaine, methadone, morphine/opiates, methamphetamine, marijuana (tetrahydrocannabinol [THC]), phencyclidine (PCP), ecstasy (3,4-methylenedioxymethamphetamine [MDMA]).
 - A urine toxicology dipstick should be used at the Baseline and Week 3 visits. At the Baseline visit, the urine toxicology dipstick should be performed before randomization.
 - Subjects who test positive and have a valid prescription for a controlled substance may be retested if they agree to abstain from the medication for the length of their participation in the study.

14.2.1 Analysis of Clinical Laboratory Variables

14.2.1.1 Observed Values and Change from Baseline

All laboratory test results will be provided in the listings. The listings will include date and study day of collection. All units will be displayed in Système International [SI] units. Out of range values will be flagged in the data listings (e.g. 'L' or 'H').

Clinical laboratory values for hematology, chemistry and urinalysis will be summarized by treatment group using descriptive statistics at Baseline, Week 3 and Week 6. The change from Baseline values will also be summarized by treatment group at Week 3 and Week 6. The overall minimum and maximum post-baseline observed and change from Baseline values will also be summarized. For hemoglobin, hematocrit and uric acid, the above summaries will be presented for each gender as well as for both genders combined. For urinalysis with categorical results (blood, protein, glucose, and ketones), the number and percentage of subjects will be tabulated by category at Baseline, Week 3 and Week 6, with the denominator being the number of subjects with non-missing values for the given parameter, visit and treatment group.

14.2.1.2 Shift Tables

Laboratory values (except the ones that were only assessed at screening and urine drug screen) will also be summarized in shift tables by treatment group, to determine the number and

percentage of subjects with values classified as below (low), within (normal), and above (high) normal ranges at Week 3, 6, overall post-baseline minimum and overall post-baseline maximum, relative to the same classification at the Baseline visit. For the by-visit shift summary, the denominator is the number of subjects with non-missing values at Baseline and the given visit for the given parameter and treatment group. For the shift to the overall post-baseline minimum or maximum, the denominator is the number of subjects with non-missing Baseline and at least one post-baseline value for the given parameter and treatment group. For hemoglobin, hematocrit and uric acid, the shift summaries will be presented for each gender as well as for both genders combined.

14.2.1.3 Potentially Clinically Important (PCI) Laboratory Values

Number and percentage of subjects with PCI laboratory values at Week 3, 6 and overall post-baseline will be summarized by treatment group for selected parameters. PCI criteria are listed in Table 2 and Table 3. For the overall post-baseline summaries of PCI values, all post-baseline values will be considered, including unscheduled and out of window values. Subjects with multiple PCI values for a given parameter will be counted only once for that parameter. For the by-visit summary, the numerator for the percentage is the number of subjects with a post-baseline PCI value for the given parameter, visit and treatment group, and the denominator is the number of subjects with non-missing values for the given parameter, visit and treatment group. For the overall post-baseline summary, the numerator for the percentage is the number of subjects with at least one post-baseline PCI laboratory value for the given parameter and treatment group, and the denominator is the number of subjects with at least one post-baseline laboratory value for the given parameter and treatment group. For hemoglobin, hematocrit and uric acid, the count and percentage of subjects with PCI values will be presented for each gender as well as for both genders combined. A listing of all subjects with any PCI values will be provided.

Table 2 Criteria for Potentially Clinically Important Laboratory Values – Hematology and Chemistry

Conventional Low PCI High PCI CLUCK Low PCI High PCI											
Analyte	Unit	Criteria	Criteria	SI Unit	Criteria	Criteria					
Hematology (whole blood)											
Hemoglobin (male)	g/dL	<11	>17	g/L	<110	>170					
Hemoglobin (female)	g/dL	<10	>17	g/L	<100	>170					
Hematocrit	%	<30	>50	L/L	< 0.3	>0.50					
Leukocyte (White Blood Cell Count)	x 10 ³ /uL	≤2.8	≥15	x 10 ⁹ /L	≤2.8	≥15					
Neutrophils	x 10 ³ /uL	≤1.5	No upper limit	x 10 ⁹ /L	≤1.5	No upper limit					
Eosinophils	%	No lower limit	≥10	L/L	No lower limit	≥.10					
Platelet Count	x 10 ³ /uL	≤75	≥700	10 ⁹ /L	≤75	≥700					
		Chemistry	(serum or plasma	n)							
ALT (SGPT)	U/L	No lower limit	≥3 X ULN	U/L	No lower limit	≥3 X ULN					
AST (SGOT)	U/L	No lower limit	≥3 X ULN	U/L	No lower limit	≥3 X ULN					
Total Bilirubin	mg/dL	No lower limit	≥1.5 ULN	umol/L	No lower limit	≥1.5 ULN					
BUN	mg/dL	No lower limit			≥10.71						
Creatine Kinase (CPK)	U/L	No lower limit	_ _		No lower limit	≥3 ULN					
Sodium	mEq/L	≤125	≥155	mmol/L	≤125	≥155					
Potassium	mEq/L	≤3.0	≥5.5	mmol/L	≤3.0	≥5.5					
Calcium, total	mg/dL	<8.0	>11.0	mmol/L	<2.0	>2.75					
Lactate Dehydrogenase (LDH)	U/L	No lower limit	≥3 X ULN	U/L	No lower limit	≥3 X ULN					
Alkaline Phosphatase	U/L	No lower limit	≥3 X ULN	U/L	No lower limit	≥3 X ULN					
Uric acid	mg/dL	No lower limit	≥8.5	umol/L	No lower limit	≥505.75					
Albumin	g/dL	≤2.6	≥6.0	g/L	≤26	≥60					
Total Protein	g/dL	≤5.0	≥10.0	g/L	≤50	≥100					
Chloride	mEq/L	≤85	≥120	mmol/L	≤85	≥120					
Glucose (random)	mg/dL	≤45.1	≥115.0	mmol/L	≤2.48	≥6.4					
Serum Creatinine	mg/dL	Not Applicable	>1.5 ULN	umol/L	Not Applicable	>1.5 ULN					
Triglycerides	mg/dL	Not Applicable	>300	mmol/L	Not Applicable	>3.39					
Gamma-Glutamyl Transferase (GGT)	U/L	Not Applicable	≥3 ULN	U/L	Not Applicable	≥3 ULN					
Phosphorus, inorganic	mg/dL	≤1.0	≥7	mmol/L	≤0.32	≥2.26					

Table 2 Criteria for Potentially Clinically Important Laboratory Values – Hematology and Chemistry (Continued)

Analyte	Conventional Unit	Low PCI Criteria	High PCI Criteria	SI Unit	Low PCI Criteria	High PCI Criteria
Total Cholesterol,	mg/dL	No lower	≥240	mmol/L	No lower	≥6,21
Fasting		limit			limit	
Hb1Ac	%	No lower	≥7	L/L	No lower	≥0.07
		limit			limit	

 Table 3
 Criteria for Potentially Clinically Important Laboratory Values - Urinalysis

Urinalysis	Low PCI Criteria	High PCI Criteria		
Blood (occult blood)	Not Applicable	≥Moderate or +2 (Q2)		
Protein	Not Applicable	≥100 mg/dL (ICON) or +2 (Q2)		
Glucose	Not Applicable	≥500 mg/dL (ICON) or +2 (Q2)		

The pregnancy results (positive or negative) for female subjects and the urine drug screen results will be presented in a listing.

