- 23. Has one or more clinical laboratory test value(s) at Screening outside the limits specified below, or any other clinically significant laboratory abnormality as determined by the Investigator:
 - a. Hemoglobin value of less than the lower limit of normal per central lab normal ranges
 - b. Aspartate aminotransferase (AST) or alanine aminotransferase (ALT) value more than 2 × the upper limit of normal (ULN)
 - c. Total bilirubin value of more than 25.7 μ mol/L (1.5 mg/dL) except in subjects with documented diagnosis of Gilbert's syndrome.
 - d. Serum creatinine more than 2 × ULN
 - e. Creatine kinase more than 1000 U/L
- 24. Has unstable diabetes mellitus (DM) as measured by a glycosylated hemoglobin $(HbA_{1c}) \ge 7\%$ at Screening

Final Version: 1.0

25. Has a clinically significant thyroid function test result at Screening (as measured by thyroid stimulating hormone [TSH] and reflex free thyroxine [T4]). If TSH is

- abnormal and the reflex free T4 is normal, the subject may be randomized 26. Has a prolactin concentration greater than or equal to 100 ng/mL at Screening
- 27. Is breastfeeding or lactating, or has a positive pregnancy test result (for subjects who are of childbearing potential)
- 28. Has a sensitivity to any compound present in pimavanserin or any metabolites or compounds listed as being present in this medication
- 29. Has received any other investigational (either approved or unapproved) drug within 30 days or five half-lives (whichever is longer) prior to Screening
- 30. Is participating in another clinical study of any investigational drug, device, or intervention
- 31. Has participated in greater than two interventional pharmaceutical clinical research studies within 6 months of Screening
- 32. Has a family member who is an employee of Acadia

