9.5.3.5 Clinical Laboratory Tests and Hormonal Assessments

The serum clinical chemistry, hematology, urinalysis and hormonal assessment results at Baseline and each post-Baseline timepoint will be summarized by treatment group. Change from Baseline values at each post-Baseline timepoint will also be summarized.

The number and percentage of subjects with potentially clinically important post-baseline laboratory values will be summarized by treatment group for selected parameters. The criteria

for potentially clinically important values are presented in Appendix C, Appendix D, and Appendix F.

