14.1 Adverse Events

All Adverse events (AEs) will be coded using MedDRA version 24.0 or higher.

An AE (classified by preferred term) will be considered a treatment-emergent AE (TEAE) if it starts after the first study dose administration and no later than last study dose date + 30 days. AEs reported on Day 1 based on Baseline (pre-dose) findings (e.g. clinically significantly abnormal vital signs, laboratory test results, or electrocardiogram parameters) will not be considered as TEAEs.

The event counts and the number and percentage of subjects reporting TEAEs in each treatment group, and the two pimavanserin groups combined will be tabulated by SOC and preferred term; and, by SOC, preferred term, and maximum severity. If more than one AE occurs with the same preferred term for the same subject, the subject will be counted only once for that preferred term using the most severe and more related occurrence for the summarization by severity and by relationship to study drug, respectively. The display in these tables will be sorted alphabetically by SOC, and then by frequency of the two pimavanserin groups combined within each SOC.

The event counts and the number and percentage of subjects with any TEAEs will also be tabulated by preferred term without SOCs within each treatment group and sorted by frequency of the two pimavanserin groups combined.

The incidence of most frequently reported (preferred terms reported by $\geq 5\%$ of subjects in any treatment group) TEAEs, TEAEs leading to discontinuation, TEAEs related to study drug, TEAEs by maximum severity, fatal TEAEs (i.e., events that cause death), serious TEAEs, and serious TEAEs related to study drug, will be summarized by SOC, preferred term, and treatment group. In addition, TEAEs by SOC, preferred term, and stimulant use will be summarized.

Version 3.0

29 July 2024

The relationship of selected AEs to COVID-19 will be assessed as detailed in the GSD and provided in the listing. Additional summaries of relationship to COVID-19 may be provided.

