14.3 Vital Signs, Height, Weight, and BMI

Vital signs, height (as measured by a stadiometer) and weight are assessed at Screening and Baseline, at all visits from Week 1 through Week 6, and at unscheduled visits. BMI will be derived as Weight (kg)/ [Height (m)]². Height and weight measurements are optional at the Week 2 and Week 5 visits if these are conducted remotely.

Vital signs, height, weight, and BMI will be summarized by treatment group using descriptive statistics at Baseline and all post-baseline visits. The change from Baseline values will also be summarized by treatment group at the post-baseline visits.

Vital sign and weight values will be considered PCI if they meet both the observed value criteria and the change from baseline criteria listed in Table 4. The number and percentage of subjects with post-baseline PCI values will be summarized by treatment group at each post-baseline visit and for overall post-baseline. For the overall post-baseline summaries, all post-baseline values will be considered, including unscheduled and out of window values. Subjects with multiple PCI values for a given parameter will be counted only once for that parameter. For the by-visit summary, the numerator for the percentage is the number of subjects with a post-baseline PCI value for the given parameter, visit and treatment group, and the denominator is the number of subjects with non-missing values for the given parameter, visit and treatment group. For the overall post-baseline summary, the numerator for the percentage is the number of subjects with at least one post-baseline PCI value for the given parameter and treatment group, and the

denominator is the number of subjects with at least one post-baseline value for the given parameter and treatment group. A listing of all subjects with any PCI values will be provided.

Table 4 Criteria for Potentially Clinically Important Vital Signs

		Criteria ^a						
Vital Sign Parameter	Unit	Observed Value	And/Or	Change Relative to Baseline				
Systolic blood pressure	mama II ca	≥140	And	Increase of ≥20				
(supine or sitting)	mmHg	≤70	And	Decrease of ≥20				
Diastolic blood pressure	ana II o	≥90	And	Increase of ≥15				
(supine or sitting)	mmHg	≤50	And	Decrease of ≥15				
D-1 (ii4i)	1	≥120	And	Increase of ≥15				
Pulse (supine or sitting)	bpm	≤50	And	Decrease of ≥15				
Weight	Va	Not Applie	abla	Increase of ≥7%				
Weight	Kg	Not Applic	aute	Decrease of ≥7%				

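### The laboratory PCI table counts values that were already PCI at Baseline together with new ones, which weakens the between-arm contrast for analytes that the entry rules leave open

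*SAP*

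**What the plan says.** For the overall post-baseline summary, SAP Section 14.2.1.3 takes as numerator "the number of subjects with at least one post-baseline PCI laboratory value for the given parameter and treatment group". The base of the percentage is equally free of any Baseline condition, since the section states that "the denominator is the number of subjects with at least one post-baseline laboratory value for the given parameter and treatment group". At Weeks 3 and 6 the rule is the same: "the numerator for the percentage is the number of subjects with a post-baseline PCI value for the given parameter, visit and treatment group", over subjects with a value at that visit. SAP Tables 2 and 3 set absolute limits, multiples of the ULN or dipstick grades, none with a change-from-Baseline condition. Protocol Section 9.5.3.5 adds no restriction; it says only that "potentially clinically important post-baseline laboratory values will be summarized by treatment group for selected parameters". The SAP addendum changes multiplicity and the tipping-point analysis, not this section.

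Other safety outputs do refer to Baseline:

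- SAP Section 14.3: "Vital sign and weight values will be considered PCI if they meet both the observed value criteria and the change from baseline criteria".
- SAP Section 14.1: "AEs reported on Day 1 based on Baseline (pre-dose) findings" are not treated as treatment-emergent.
- SAP Section 14.2.1.2: shift tables relative to Baseline give the "percentage of subjects with values classified as below (low), within (normal), and above (high) normal ranges".

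**The concern.** A child who is beyond a PCI limit before the first dose and stays there is tabulated as a post-baseline PCI case. Such children should be about equally frequent in each randomized arm, so they add a similar number of cases to each row and make the arms look more alike.

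No planned table separates the two kinds of case. The shift tables use normal-range classes. A normal-to-high shift does not say whether the PCI limit was crossed, and a child who moves from slightly high to PCI stays in the high-to-high cell. Change-from-Baseline summaries are not tied to PCI limits. What is missing is a rate, per arm, of new PCI values. With no formal safety testing planned, readers will judge from the tabulated percentages.

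**Working it through.** **1. Can a child enter already PCI?** Entry rules are from Protocol Section 4.2 (exclusion criteria 23 and 24, applied at Screening); PCI limits are from SAP Table 2.

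| Analyte | Entry rule | PCI limit | Baseline PCI possible? |
|---|---|---|---|
| Creatinine | "Serum creatinine more than 2 × ULN" is excluded | >1.5 ULN | Yes, between 1.5 and 2 x ULN |
| Bilirubin | >1.5 mg/dL excluded, Gilbert's syndrome exempt | ≥1.5 ULN | Yes, in Gilbert's syndrome |
| Eosinophils | no numeric limit | ≥10% | Yes |
| Neutrophils | no numeric limit | ≤1.5 x 10³/uL | Yes |
| Random glucose | no numeric limit; fasting not required (Protocol 6.4.5) | ≥115 mg/dL | Yes |
| Triglycerides, cholesterol | no numeric limit | >300, ≥240 mg/dL | Yes |
| ALT, AST | >2 x ULN excluded | ≥3 x ULN | Near zero |
| Low haemoglobin | below lower limit of normal excluded | <11 (male), <10 (female) g/dL | Near zero |
| HbA1c | ≥7% (unstable diabetes) excluded | ≥7% | Near zero |

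Criterion 23 also excludes any other laboratory abnormality that the Investigator judges clinically significant. This narrows the open rows but does not close them.

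**2. Formula.** The plan states no expected PCI rate, so there is no figure to reproduce. Let b be the proportion PCI at Baseline (equal in both arms in expectation), r the share of these who are PCI again after Baseline, and i the incidence of new PCI among the rest.

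- Tabulated rate in an arm = b·r + (1 − b)·i
- Tabulated difference = (1 − b)·(i_drug − i_placebo)

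The difference shrinks only by the factor (1 − b), whatever r is. The ratio shrinks more, because b·r is added to both rates.

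**3. Illustration.** Assume i = 6% on drug and 2% on placebo, so the true ratio is 3.0 and the true difference 4.0 points. With full persistence (r = 1):

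| b | Drug | Placebo | Ratio | Difference |
|---|---|---|---|---|
| 2% | 0.02 + 0.98 x 0.06 = 7.9% | 0.02 + 0.98 x 0.02 = 4.0% | 1.99 | 3.9 points |
| 5% | 0.05 + 0.95 x 0.06 = 10.7% | 0.05 + 0.95 x 0.02 = 6.9% | 1.55 | 3.8 points |
| 10% | 0.10 + 0.90 x 0.06 = 15.4% | 0.10 + 0.90 x 0.02 = 11.8% | 1.31 | 3.6 points |

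In counts at b = 5%, with the planned 76 per group: 76 x 0.05 = 3.8 pre-existing cases in each arm, plus 76 x 0.95 x 0.06 = 4.3 new cases on drug and 76 x 0.95 x 0.02 = 1.4 on placebo.

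**4. Sensitivity to persistence.** With r = 0.6 and b = 5%, the rates are 0.03 + 0.057 = 8.7% and 0.03 + 0.019 = 4.9%, a ratio of 1.78 instead of 1.55.

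**5. Sensitivity to incidence.** With i = 15% versus 5% (ratio 3.0, difference 10.0 points) and full persistence, b = 5%, 10% or 20% gives ratios of 1.97, 1.62 or 1.33 and differences of 9.5, 9.0 or 8.0 points. With r = 0.6 the ratios are 2.23, 1.86 and 1.50.

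**6. After the fix.** Restricted to subjects not PCI at Baseline, the expected rates are i itself (6% versus 2%, ratio 3.0) whatever b and r are, on about 76 x (1 − b) subjects per arm: 72 at b = 5%, 68 at b = 10%.

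**The case against.** The strongest reply is that the SAP does what the protocol says. Protocol Appendix C sets absolute laboratory limits, Appendix F adds a change criterion for vital signs only, and the table is labelled post-baseline, not treatment-emergent. This stands: there is no contradiction between the documents. Nor is the vital-sign rule a full model, since a systolic pressure that rises from 140 to 160 mmHg still counts there.

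A second reply is that the information exists elsewhere. All laboratory results and all PCI subjects are listed, so new and old values can be separated child by child. That is true, but no table then gives the rate per arm.

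A third concerns size. Prevalence, incidence and persistence are all assumed, full persistence is the worst case, and the absolute difference barely moves. This also stands.

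A reader might infer four stronger things that the documents do not support:

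- That any real laboratory signal is diluted. The entry rules make the effect near zero for ALT/AST, low haemoglobin and HbA1c.
- That this is the main categorical laboratory output. The SAP ranks no table, and the shift tables are categorical too.
- That the table is biased towards one arm. Randomization balances Baseline PCI in expectation, so the effect is attenuation.
- That QRS and PR need the same treatment. Exclusion criterion 18 removes PR above 220 ms and intraventricular conduction delay with QRS above 110 ms, against PCI limits of 220 and 120 ms, so almost nothing is left to separate.

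Finally, replacing the planned rows would do harm: a child whose creatinine goes from 1.6 to 4 x ULN would leave the table. The remedy should therefore be an addition.

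**Conclusion.** The point holds for analytes whose entry rules let in children who are already PCI. For these, the planned percentages mix persistent and new PCI values and attenuate the between-arm contrast. The direction is certain when there is a true excess on drug and at least some Baseline PCI values persist equally across arms. The size is not known from the documents. The ratios in the working are derived illustrations; the SAP itself plans only numbers and percentages. The absolute difference keeps the fraction 1 − b, which is 90% to 98% over the 2% to 10% range of assumed Baseline prevalence. No efficacy conclusion or formal test is affected. This is a worthwhile, low-priority improvement to a descriptive safety table.

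**What to change.** Keep the planned rows in SAP Section 14.2.1.3 and add a treatment-emergent PCI row for each analyte and direction, by visit and overall:

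- **Numerator:** subjects with a post-baseline PCI value (at that visit, or at least one overall) and a non-missing Baseline that is not PCI in the same direction.
- **Denominator:** subjects with a non-missing Baseline that is not PCI in that direction and a post-baseline value (at that visit, or at least one overall).

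Subjects who are PCI at Baseline stay in the planned rows and the listing, so that worsening remains visible. Those with a missing Baseline drop out of the added row only. No change is needed for QRS or PR in Section 14.4.

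The cost is a few lines of SAP text and a filter in the table program, using Baseline laboratory data already collected. The downside is one extra row per analyte and direction, with denominators that differ slightly between analytes.

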Appendix C Criteria for Identifying Potentially Clinically Important Laboratory Values

Analyte	Conventional Unit	Low PCI Criteria	High PCI Criteria
Hematology (whole blood)	Cint		
Hemoglobin (Male)	g/dL	<11	>17
Hemoglobin (Female)	g/dL	<10	>17
Hematocrit (Both)	%	<30	>50
Leukocyte (White Blood Cell	$\times 10^3/\text{uL}$	≤2.8	≥15
Count)			
Neutrophils	$\times 10^3/\text{uL}$	≤1.5	No upper limit
Eosinophils	%	≥10%	No lower limit
Platelet Count	× 10 ³ /uL	≤75	≥700
Chemistry (serum or plasma)			
ALT (SGPT)	U/L	No lower limit	≥3 × ULN
AST (SGOT)	U/L	No lower limit	≥3 × ULN
Gamma-Glutamyl Transferase (GGT)	U/L	No lower limit	≥3 ULN
Lactate Dehydrogenase (LDH)	U/L	No lower limit	≥3 × ULN
Alkaline Phosphatase	U/L	No lower limit	≥3 × ULN
Total Bilirubin	mg/dL	No lower limit	≥1.5 ULN
СРК	mg/dL	No lower limit	≥3 ULN
BUN	mg/dL	No lower limit	≥30.0
Serum Creatinine	mg/dL	Not Applicable	>1.5 ULN
Sodium	mEq/L	≤125	≥155
Potassium	mEq/L	≤3.0	≥5.5
Calcium, total	mg/dL	<8.0	>11.0
Chloride	mEq/L	≤85	≥120
Phosphorous, inorganic	mg/dL	≤1.0 mg/dL	≥4.5 mg/dL
Magnesium	mEq/L	≤0.7 mEq/L	≥5.0 mEq/L
Uric acid	mg/dL	No lower limit	≥8.5
Albumin	g/dL	≤2.6	≥6.0
Total Protein	g/dL	≤5.0	≥10.0
Glucose (random)	mg/dL	≤45.1	≥115.0
HbA _{1c}	%	No lower limit	≥7%
Total Cholesterol, Fasting	mg/dL	No lower limit	≥240 mg/dL
Urinalysis			
Blood (occult blood)		Not Applicable	≥ Moderate
Protein			
Trotein	mg/dL	Not Applicable	≥100 mg/dL

Abbreviations: ALT (SGPT)=alanine aminotransferase (serum glutamic-pyruvic transaminase); AST (SGOT)=aspartate aminotransferase (serum glutamic-oxaloacetic transaminase); BUN=blood urea nitrogen; CPK=creatine phosphokinase; HbA_{1c}=glycosylated hemoglobin; PCI=potentially clinically important; ULN=upper limit of normal.

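### The two low-glucose limits in SAP Table 2 do not match: 45.1 mg/dL is about 2.50 mmol/L, not the 2.48 mmol/L printed beside it

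*SAP*

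**What the plan says.** Protocol Appendix C lists the glucose criterion in conventional units only: "Glucose (random) mg/dL ≤45.1 ≥115.0". SAP section 14.2.1.3, Table 2, repeats those limits and adds SI limits in the same row: "Glucose (random) mg/dL ≤45.1 ≥115.0 mmol/L ≤2.48 ≥6.4".

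Four further statements in the SAP bear on which limit is used:

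- Section 14.2.1.3 points to the tables for the criteria: "PCI criteria are listed in Table 2 and Table 3". Table 2 carries both unit systems, and the section does not say which one sets the flag.
- Section 14.2.1.1, in its paragraph on listings, says: "All units will be displayed in Système International [SI] units".
- Section 14.2 says of local laboratories: "Local laboratory results and the associated normal ranges will be converted to SI units".
- Section 14.2 then says what enters the analyses: "Only central lab and normalized local lab results will be used for summary of change from baseline, shift, and potentially clinically important (PCI) analyses".

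Section 19 declares no change to the analyses in the protocol. The version history in section 21.4 records PCI cutoff updates for phosphate and urinalysis, and none for glucose.

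**The concern.** The two figures in the low-glucose cell are presented as one limit in two units, so they should classify every result in the same way. They do not, because the SI limit is the stricter of the two. A result just under the protocol's limit can be PCI in mg/dL and unflagged in mmol/L. The discrepancy runs one way: using the SI limit in place of the mg/dL limit can only remove low-glucose flags.

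At stake is agreement between the SAP output and a review of the same data against Appendix C. The outputs concerned are the PCI counts at Week 3, at Week 6 and overall post-baseline, and the listing of subjects with any PCI value. With two unequal limits and no stated precedence, the count depends on a programming choice that the SAP leaves open.

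**Working it through.** **Inputs**

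- Low limit 45.1 mg/dL: Protocol Appendix C and SAP Table 2.
- Low limit 2.48 mmol/L: SAP Table 2.
- High pair 115.0 mg/dL and 6.4 mmol/L: SAP Table 2 (115.0 is also in Appendix C).
- Molar mass M of glucose: not in the documents. Assumed 180.16 g/mol, with 180.0 to 180.2 tried.

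**1. Trying to reproduce 2.48.** The formula is mmol/L = mg/dL × 10 / M.

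- 45.1 × 10 / 180.16 = 2.503. Over the range of M the result is 2.503 to 2.506, so 2.48 is not reproduced.
- 2.48 does follow from a coarse factor of 0.055: 45.1 × 0.055 = 2.4805. The same factor turns 115.0 into 6.325, which does not round to the stated 6.4.

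**2. The other direction.** 2.48 × 180.16 / 10 = 44.68 mg/dL (44.64 to 44.69 over the range of M). The two low limits differ by 45.1 − 44.68 = 0.42 mg/dL, or 0.42 / 45.1 = 0.9%.

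**3. The row on its own, with no outside constant.** Allow each SI figure its rounding interval.

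| Pair | Smallest factor | Largest factor |
|---|---|---|
| Low (45.1 and 2.48) | 2.475 / 45.1 = 0.0549 | 2.485 / 45.1 = 0.0551 |
| High (115.0 and 6.4) | 6.35 / 115.0 = 0.0552 | 6.45 / 115.0 = 0.0561 |

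The intervals do not overlap. The high pair's interval puts 45.1 mg/dL at 2.490 to 2.530 mmol/L, wholly above 2.48.

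**4. What falls between the limits.**

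- 45 mg/dL is 45 × 10 / 180.16 = 2.498 mmol/L (2.497 to 2.500 over the range of M). It meets the mg/dL criterion and fails the SI one.
- 44 mg/dL is 2.442 mmol/L and is flagged by both. With whole-number mg/dL results, 45 is therefore the only low reading affected.

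**5. Other converted limits in Table 2.** These use standard molar masses, again assumed. The urea nitrogen value of 30 mg/dL is taken from Appendix C.

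| Limit | Converted | Stated |
|---|---|---|
| Calcium 8.0 mg/dL | 2.00 | 2.0 |
| Calcium 11.0 mg/dL | 2.745 | 2.75 |
| Uric acid 8.5 mg/dL | 505.6 | 505.75 |
| Urea nitrogen 30 mg/dL | 10.71 | 10.71 |
| Triglycerides 300 mg/dL | 3.39 | 3.39 |
| Total cholesterol 240 mg/dL | 6.207 | 6.21 |
| Phosphorus 7 mg/dL | 2.26 | 2.26 |
| Glucose 115.0 mg/dL | 6.383 | 6.4 |
| Glucose 45.1 mg/dL | 2.503 | 2.48 |

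The upper calcium limit and the uric acid limit reflect coarse factors (0.25 and 59.5). Their errors are about 0.2% and 0.03%, against 0.9% for low glucose, which is the largest in the table.

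**The case against.** The strongest reply is that nothing in the SAP says the SI figure sets the flag. Table 2 prints both columns, and the SI sentence in section 14.2.1.1 concerns how listings are displayed. Section 14.2 converts local results to SI before they enter the PCI analysis, which makes SI use likely but not certain. This stands: the loss of flags is conditional on the SI column being programmed.

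A reader might also infer that the SAP has dropped the protocol's criterion. It has not, because 45.1 mg/dL is printed in the same row. The defect is that the row contains two different limits.

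Nor is a missed boundary value peculiar to this cell. A reading of 115 mg/dL converts to 6.383, below the SI limit of 6.4. Uric acid of 8.5 mg/dL and cholesterol of 240 mg/dL also fall just short of their SI limits. The 115.0 and 240 cases are ordinary rounding, and uric acid is a coarse factor with a trivial error. What sets low glucose apart is a mismatch beyond rounding that contradicts the high pair in its own row.

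Finally, the practical effect may be nil. Safety results are descriptive. All laboratory results are listed with out-of-range flags, and post-baseline minima appear in both the summaries and the shift tables, so a 45 mg/dL value would remain visible. The documents give no glucose distribution from which to estimate an under-count. All of this stands, and it limits the size of the point. It does not make the two limits equal.

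**Conclusion.** The point holds as a minor arithmetic error. The low-glucose limits in SAP Table 2 are not equivalent. This follows from the row alone, and the size (0.42 mg/dL, 0.9%) rests only on the assumed molar mass.

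Any effect on the PCI counts requires that the SI column be programmed and that a result fall above 44.68 and up to 45.1 mg/dL. The primary analysis and all formal testing are untouched.

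Three stronger readings are not supported:

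- That subjects will certainly be under-counted. The documents state neither the column used nor how glucose values are distributed.
- That the working limit drops to 2.4 mmol/L (2.4 × 18.016 = 43.2 mg/dL). That would need SI results reported to one decimal, and no reporting precision is given.
- That the limit was changed on purpose. The row keeps 45.1 mg/dL, and the version history mentions no glucose change.

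This says nothing about which glucose threshold is clinically appropriate, only that the two printed limits must be reconciled.

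**What to change.** Make the SI criterion reproduce the protocol's 45.1 mg/dL, and say in section 14.2.1.3 which column of Table 2 sets the flag. There are two ways to do it:

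- **Apply the mg/dL limit to results expressed in mg/dL.** This is the cleaner choice. It reproduces Appendix C directly and would also remove the rounding gap at the high limit.
- **Replace 2.48 with the equivalent of 45.1 mg/dL.** Either hold 45.1 × 10 / 180.16 (about 2.503) at full precision, or use 2.50 on results first rounded to two decimals. The rounding rule must be written down: at full precision a reading of exactly 45.1 mg/dL is 2.503 and would still fail a limit of 2.50. If SI results come to only one decimal, a limit of 2.50 admits every result reported as 2.5, which covers true values up to about 2.55 × 18.016 = 45.9 mg/dL.

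The cost is one figure in Table 2, one sentence in section 14.2.1.3 and one constant in the PCI program. No data collection changes.
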